## **5.0 Study Treatment**

### **5.1 Regimens, Administration, and Duration**

Study treatment is open label bictegravir + tenofovir alafenamide + emtricitabine (only bictegravir is investigational).

At entry participants will be randomized 1:1 by the study team to:

ARM A (immediate switch): Switch current ART to bictegravir + tenofovir alafenamide + emtricitabine for 48 weeks

or

ARM B (no switch): Continue current therapy for 48 weeks

If randomized to ARM A at study entry, the subject will substitute bictegravir + tenofovir alafenamide + emtricitabine for their entry ART regimen.

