## **7.0 Toxicity Management**

Criteria for participant management, dose interruptions, modifications, and discontinuation of drug treatment will be mandated only for toxicities attributable to study drug (for Arm A participants). Toxicities due to drugs in the background regimen/entry regimen (for Arm B participants) should be managed according to standard clinical practice, with the goal of maintaining continuous therapy, if possible.

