### **7.2 Grade 3 Toxicity**

Participants who develop a Grade 3 AE or toxicity should have all antiretroviral medications, including study drug, withheld unless the investigator has compelling evidence that the AE has NOT been caused by the study drug. The study chair ([name]) should be notified of any Grade 3 or greater toxicity. The subject should be re-evaluated closely until the AE returns to Grade  $\leq 2$ , at which time study drug may be reintroduced at the discretion of [name] or according to standard practice.

If the same Grade 3 AE recurs within 4 weeks following reintroduction and it is thought to be related possibly, probably, or definitely to study drug, then study drug must be permanently discontinued. If the same Grade 3 AE recurs after 4 weeks but is not believed to be related to study drug, the management scheme outlined above may be repeated.

Participants experiencing Grade 3 or greater AEs (requiring permanent discontinuation of study drug) should be followed closely for resolution of the AE to Grade  $\leq 2$ , and [name] must be consulted.

Participants with Grade 3 asymptomatic laboratory abnormalities in cholesterol, triglycerides or bilirubin (if on atazanavir) may continue study drug.

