### **7.3 Grade 4 Toxicity**

Participants who develop a Grade 4 symptomatic AE or toxicity will have study drug discontinued. If the site investigator has compelling evidence that the AE has not been caused by the study drug, dosing may resume when the AE has resolved and after consulting [name]. Participants experiencing Grade 4 AEs requiring permanent discontinuation of study drug should be followed closely until resolution of the AE to Grade  $\leq 2$ , and [name] must be consulted.

Participants with Grade 4 asymptomatic laboratory abnormalities in cholesterol or triglycerides may continue study drug.

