## **8.0 Criteria For Discontinuation**

### **8.1 Permanent Study Drug Discontinuation**

Study drug discontinuation can occur for the following reasons:

- Drug-related toxicity requiring permanent discontinuation (see Section 7.1).
- Requirement for prohibited concomitant drugs (see section 5.4).
- Request by participant to terminate treatment.
- Confirmation of virologic failure (two measurements of HIV-1 RNA  $>200$  copies/mL at least 2 weeks apart).
- Clinical reasons believed life-threatening by the physician, even if not addressed in the toxicity section of the protocol.
- Participant repeatedly noncompliant with study drug as prescribed.
- Participant discontinues study drug for  $\geq 14$  consecutive days (Arm A).
- Participant discontinues background entry regimen for  $\geq 14$  consecutive days (Arm B).
- Failure by the participant to attend  $\geq 2$  consecutive study visits.

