## 9.3 Primary Endpoint Assessments

The safety (frequency of maintaining HIV-1 RNA <50 copies/mL) and tolerability (frequency of study drug discontinuation due to study-drug related AEs and frequency of study-drug related ≥ Grade 3 lab or clinical events whether or not study drug was discontinued) of bictegravir + tenofovir alafenamide + emtricitabine in HIV-infected TW on female hormone therapy vs continued ART.

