### **9.6.2 Occurrence of Study-Related AE**

The number of participants who experience treatment-related AE from the first day of study treatment to Week 48 will be reported by arm.

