## **10.4 Serious Adverse Event Reporting**

The serious adverse event (SAE) reporting requirements and definitions for this study will be in keeping with local McGovern School of Medicine policies and in keeping with the sponsor's requirement. The study agent for SAE reporting is bictegravir + tenofovir alafenamide + emtricitabine. SAEs must be documented on the Serious Adverse Event Reporting form (SAE Reporting Form) available in the Manual of Procedure. [name] must be notified for any Grade 3 or greater toxicity that does not have a clearly documented etiology of not related to study drug. All Grade 4 events, death, persistent or significant disability/incapacity, hospitalization or prolongation of hospitalization, or event that the site investigator deems medically significant and thought to be related possibly, probably, or definitely related to study drug must be reported by completing and faxing the SAE Reporting form to [contact].

SAEs must be reported during the protocol-defined SAE Reporting period, which is from enrollment until four weeks following the subject's last dose of study drug. After the end of the protocol-defined SAE Reporting Period stated above, the site must report serious, unexpected, clinically-suspected adverse drug reactions if the site staff becomes aware of the event on a passive basis, i.e., from publicly available information.

All confirmed virologic failures will be reported immediately to the SMC. The SMC will also receive quarterly SAE reports for review.

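### The AE counts in 9.3 and 9.6.2 include only events judged treatment related in an open-label trial, and the final analysis plans no all-cause AE count by arm

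*Combined protocol and SAP*

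**What the plan says.** Section 9.3 defines tolerability by two frequencies. One is study drug discontinuation because of related AEs. The other is the "frequency of study-drug related ≥ Grade 3 lab or clinical events whether or not study drug was discontinued". The only AE count in the final analysis is in 9.6.2: "The number of participants who experience treatment-related AE from the first day of study treatment to Week 48 will be reported by arm".

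The reference product for relatedness is the switch regimen. Section 5.1 reads "Study treatment is open label bictegravir + tenofovir alafenamide + emtricitabine (only bictegravir is investigational", and 10.4 adds: "The study agent for SAE reporting is bictegravir + tenofovir alafenamide + emtricitabine". Arm B does not take it.

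Other sections treat the Arm B entry regimen as the counterpart of study drug. Section 7.0 says toxicities from the "background regimen/entry regimen (for Arm B participants) should be managed according to standard clinical practice, with the goal of maintaining continuous therapy, if possible". Section 8.1 lists "Participant discontinues background entry regimen for" 14 or more consecutive days beside the same rule for study drug in Arm A, and 9.6.1 pairs the two in the same way. Neither 9.3 nor 9.6.2 carries that pairing over.

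Without a relatedness filter, 6.5 records post-entry signs and symptoms of Grade 2 or higher and all confirmed or probable diagnoses, and 6.6 records laboratory values. Section 9.5 has AEs tabulated by arm for monthly and quarterly team review and for an interim look by an independent committee. Section 9.6.3 summarises treatment discontinuation by arm, with reasons.

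**The concern.** Causality is judged by people who know who switched. If the judgement leans differently by arm, the related-only counts can differ when the events do not, or agree when the events differ.

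This population makes the question practical. Everyone enrolled takes female hormone therapy (4.1.6), and section 2.1 links that therapy to cardiovascular and thromboembolic events. Such an event therefore has a ready explanation other than ART. Once attributed wholly to hormones, it leaves both planned counts, whichever arm it occurred in.

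The yardstick is also not stated for Arm B. Read literally, no Arm B event can be related to study drug, and the 9.6.2 window, which opens on the first day of study treatment, has no start date there. On the more natural reading, treatment in Arm B means the entry ART. The text of the two sections does not settle it.

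At stake is whether the final report of a trial whose primary objective is safety shows, by arm, how many participants had a serious or severe event.

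**Working it through.** The plan states no AE rate or AE precision figure, so there is nothing of its own to reproduce here. The check has two parts.

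**1. Where an event judged unrelated to ART would appear.**

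| Planned output | Relatedness filter? | Shows the event? |
|---|---|---|
| 9.3, discontinuation component | yes | no |
| 9.3, Grade 3 or higher component | yes | no |
| 9.6.2, AE count | yes | no |
| 9.6.3, discontinuations | no | only if treatment was discontinued, including 14 or more consecutive days off (8.1) |
| 9.5, monitoring reports | no | yes, but not as a final result |

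The 9.6.3 route is not the same in both arms. In Arm A, 7.2 has ART "withheld unless the investigator has compelling evidence that the AE has NOT been caused by the study drug", and after a symptomatic Grade 4 event judged not caused by study drug, 7.3 says "dosing may resume when the AE has resolved and after consulting" the study chair. Some Arm A events will therefore reach 9.6.3 through a long hold. In Arm B the aim is to keep ART going. The events that can miss every planned final count are Arm B events with ART continued, and Arm A events judged unrelated with no hold or one under 14 days.

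**2. Illustrations at 24 per arm (enrolled number from 9.1).** Exact two-sided 95% intervals (Clopper-Pearson):

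- 0/24: upper limit 1 − 0.025^(1/24) = 0.142, so 0% to 14.2%.
- 1/24 = 4.2%: lower limit 1 − 0.975^(1/24) = 0.001; upper limit solves P(X ≤ 1) = 0.025, giving 0.211. So 0.1% to 21.1%.
- 2/24 = 8.3%: limits solve P(X ≥ 2) = 0.025 and P(X ≤ 2) = 0.025, giving 1.0% to 27.0%.

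Three event patterns, chosen to show the mechanism:

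- *Omission.* One Arm B event, ART continued, attributed to hormones: 1/24 (0.1% to 21.1%) all-cause becomes 0/24 (0% to 14.2%).
- *A difference created.* Two participants per arm with the same event, judged related in A and unrelated in B: 2/24 − 2/24 = 0 becomes 2/24 − 0/24 = 8.3 points.
- *A difference hidden.* Two events in A, none in B, both attributed to hormones: 2/24 − 0/24 = 8.3 points becomes 0/24 − 0/24 = 0.

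A 2 v 0 split is far from a test result. With pooled p = 2/48 = 0.0417, z = 0.0833 / √(0.0417 × 0.9583 × 2/24) = 0.0833 / 0.0577 = 1.44, below 1.96.

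As a range under pure assumption, let the all-cause proportion be equal in both arms at 10%, 20%, 30% or 40%, and enumerate the Pearson chi-square exactly at 24 per arm:

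| Share judged related (A v B) | Rejection at 10%, 20%, 30%, 40% |
|---|---|
| all events counted | 4.7%, 5.4%, 5.2%, 5.5% |
| 50% v 50% | 1.8%, 4.7%, 5.4%, 5.4% |
| 70% v 30% | 4.3%, 14.3%, 22.0%, 29.4% |

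At a 20% rate the last row corresponds to 24 × 0.2 × 0.7 = 3.4 v 24 × 0.2 × 0.3 = 1.4 expected participants. Equal attribution produces no false difference; unequal attribution does. The documents support none of these rates or shares, so the table shows direction only.

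**The case against.** The best defence is that the information is not lost. Events are recorded in both arms whatever their cause, all AEs are tabulated by arm each quarter, and an independent committee sees AE summaries by arm and quarterly SAE reports. Section 9.6 also leaves further analysis planning to the study team, and this is a small pilot that calls its analysis exploratory. All of that stands. It narrows the point to the planned final results, where no all-cause AE count appears, and it makes the remedy cheap. It does not remove the point, because monitoring tables are not a commitment to report.

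A reader might infer that every event with a hormonal explanation disappears. The documents do not support that. Attribution need not be exclusive: 10.4 uses possible, probable and definite relatedness for SAE reporting, so an event judged possibly due to both causes could still count. Only events judged unrelated to ART drop out.

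A reader might also infer that Arm B can contribute no events at all. That is the literal reading of 5.1 with 9.3, but 7.0, 8.1 and 9.6.1 point to the entry regimen as its counterpart. The fair statement is that the definition is missing.

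It may also be said that related-only counts are usual. They may be kept; the difficulty is having them alone.

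**Conclusion.** The point holds for the two AE components of the 9.3 tolerability endpoint and for the 9.6.2 count. Both depend on open-label attribution whose reference regimen is not defined for Arm B, and nothing in 9.6 to 9.6.3 counts AEs regardless of cause. The change should be made; the trial does not depend on it.

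The size cannot be derived. The 1/24 and 2/24 cases illustrate that, at 24 per arm, one or two attribution decisions move a reported proportion by 4.2 or 8.3 points. The intervals overlap widely, so the secure claim is about what gets reported.

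Two stronger conclusions should be resisted. One is that the primary comparison has an inflated false-positive rate: that needs an AE rate and an attribution imbalance, and the documents give neither. The other is that the whole safety assessment is compromised: the HIV-1 RNA component of 9.3, the laboratory secondary endpoints in 9.4 and the discontinuation summary in 9.6.3 do not use this filter.

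**What to change.** In 9.6.2, keep the by-arm count of treatment-related AEs at any recorded grade, and state that treatment in Arm B means the entry ART regimen. Put the same definition in 9.3, so that the endpoint and the table use one rule.

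Add to 9.6.2 a descriptive count by arm, from the entry visit to Week 48 or the last study visit and regardless of attribution, of participants with (a) any Grade 3 or higher clinical or laboratory event and (b) any SAE, including deaths and hospitalizations. Starting at entry gives both arms the same opening date.

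The cost is a few sentences and one table. Line (a) uses data that 6.5 and 6.6 already collect and 9.5 already tabulates. Line (b) is also available if 10.4 is read as making deaths, Grade 4 events and hospitalizations reportable whatever the cause. That section can be read otherwise, and it defers to local and sponsor policies not shown. Its reporting period ends four weeks after the last dose of study drug, which Arm B does not take. A clause fixing the Arm B window would help but is optional and separate from this point.

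The downside is that the table will show some events the drug did not cause. Presenting it as descriptive, beside the related-only count, deals with that.

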### **9.6.3 Proportion of Participants who Discontinue Study Treatment**

Proportion of participants who discontinue the study treatment prior to Week 48 will be summarized by arm. Reasons for discontinuing study drug will be listed.

## **10.0 Data Collection, Monitoring, and Adverse Event Reporting**

### **10.1 Records to Be Kept**

Data will be collected onto CRFs, and will be labeled only with a subject's study ID number. CRFs will be stored in a locked cabinet available only to study personnel for a period of time determined by pertinent policies and regulations, and for at least two years after study discontinuation. The key linking study ID #s to personal identifying information will be kept in a separate locked cabinet accessible only by [name] and the study coordinator.

### **10.2 Role of Data Management**

Instructions concerning the recording of study data on CRFs will be provided by [name]. The site is responsible for keying the data in a timely fashion within 14 days.

## **10.3 Clinical Site Monitoring and Record Availability**

Local monitoring of this investigator-initiated, non-IND study may occur according to standard McGovern School of Medicine policies, or by the study sponsor.

## **10.4 Serious Adverse Event Reporting**

The serious adverse event (SAE) reporting requirements and definitions for this study will be in keeping with local McGovern School of Medicine policies and in keeping with the sponsor's requirement. The study agent for SAE reporting is bictegravir + tenofovir alafenamide + emtricitabine. SAEs must be documented on the Serious Adverse Event Reporting form (SAE Reporting Form) available in the Manual of Procedure. [name] must be notified for any Grade 3 or greater toxicity that does not have a clearly documented etiology of not related to study drug. All Grade 4 events, death, persistent or significant disability/incapacity, hospitalization or prolongation of hospitalization, or event that the site investigator deems medically significant and thought to be related possibly, probably, or definitely related to study drug must be reported by completing and faxing the SAE Reporting form to [contact].

SAEs must be reported during the protocol-defined SAE Reporting period, which is from enrollment until four weeks following the subject's last dose of study drug. After the end of the protocol-defined SAE Reporting Period stated above, the site must report serious, unexpected, clinically-suspected adverse drug reactions if the site staff becomes aware of the event on a passive basis, i.e., from publicly available information.

All confirmed virologic failures will be reported immediately to the SMC. The SMC will also receive quarterly SAE reports for review.

## **11.0 Human Subjects**

### **11.1 Institutional Review Board Review and Informed Consent**

This protocol, the informed consent document, and any subsequent modifications will be reviewed and approved by the IRB responsible for oversight of the study. A signed consent form will be obtained prior to screening and prior to study continuation should protocol modifications be required that led to the development of an amended informed consent document. The consent form will describe the purpose of the study, the procedures to be followed, and the risks and benefits of participation. A copy of the signed consent form will be given to the participant, and this fact will be documented in the study record. Consent forms will be available in English and Spanish.

### **11.2 Subject Confidentiality**

All laboratory specimens, evaluation forms, reports, and other records that leave the site will be identified by coded number only to maintain participant confidentiality. All records will be kept locked. All computer entry and networking programs will be done with coded numbers only. Clinical information will not be released without written permission of the subject, except as necessary for monitoring by IRB, SMC, FDA, the office for the protection of human subjects, or the sponsor or their designee.

### **11.3 Study Discontinuation**

The study may be discontinued at any time by the IRB, the sponsor, the FDA, the office for the protection of human subjects, or other government agencies as part of their duties to ensure that research participants are protected.

## **12.0 Publication of Research Findings**

Any presentation, abstract, or manuscript will be made available for review by Gilead Sciences prior to submission.

### **13.0 Biohazard Containment**

As the transmission of HIV and other blood-borne pathogens can occur through contact with contaminated needles, blood, and blood products, appropriate blood and secretion precautions will be employed by all personnel in the drawing of blood and shipping and handling of all specimens for this study, as currently recommended by the Centers for Disease Control and Prevention and the National Institutes of Health.

All dangerous goods materials, including diagnostic specimens and infectious substances, will be transported according to the instructions detailed in the International Air Transport Association (IATA) Dangerous Goods Regulations.

### **14.0 Proposed Sites**

The TSHC has experience conducting metabolic studies, HIV expertise and the available population of TW.

